16. SOURCE DOCUMENTS/DATA

16.1 Recording of source data

Data collection is the responsibility of the clinical trial staff at the site under the supervision of the site investigator. The investigator is responsible for ensuring the accuracy, completeness, legibility, and timeliness of the data reported. All source documents should be completed in a neat, legible manner to ensure accurate interpretation of data.

Data recorded in the electronic case report form (eCRF) derived from source documents should be consistent with the data recorded on the source documents.

16.2 Direct access to source document/data

The Investigators or designated must permit trial-related monitoring, audits, Ethics Committee/Institutional Review Board review or regulatory inspection, providing direct access to source data/documents.

17. STUDY MONITORING

Monitoring will be performed by the CRO [REDACTED] who has been designated by Chiesi. It is understood that the monitor(s) will contact and visit the Investigator/centre before the study, regularly throughout the study and after the study had been completed, and that they will be permitted to inspect the various study records: case reports form, Investigator study file and source data, provided that patient confidentiality is respected.

The purposes of these visits are:

- To assess the progress of the study;
- To review the compliance with the study protocol;

Clinical Study Code No.: CLI-050000-04	Version No.: 4.0
EUDRACT No.: 2020-002632-75 – IND No: 153286	Date: 02 MAR 2021

- To discuss any emergent problem;
- To validate the contents of the CRFs against the source documents;
- To assess the status of drug storage, dispensing and retrieval;
- Prior to each monitoring visit, the Investigator or staff will record all data generated since the last visit on the case report forms. The Investigator and/or study staff will be expected to be available for at least a portion of the monitoring visit to answer questions and to provide any missing information.
- It is possible that the Investigator site may be audited by Sponsor personnel or regulatory national and/or international regulatory agencies during and after the study has been completed.

Given the current pandemic situation the proper approaches will be implemented remotely to allow the performance of the monitoring activities.

18. QUALITY ASSURANCE

The R&D Quality Assurance Department of Chiesi may perform an audit at any time according to the Sponsor's Standard Operating Procedures, in order to verify whether the study is being conducted in agreement with Good Clinical Practices and the protocol.

19. INSURANCE AND INDEMNITY

Chiesi holds and will maintain an adequate insurance policy covering damages arising out of Chiesi's sponsored clinical research studies.

Chiesi will indemnify the Investigator and hold him/her harmless for claims for damages arising out of the investigation, in excess of those covered by his/her own professional liability insurance, providing that the drug was administered under his/her or deputy's supervision and in strict accordance with accepted medical practice and with the study protocol.

The Investigator must notify Chiesi immediately upon notice of any claims or lawsuits.

20. CONFIDENTIALITY

All study documents are provided by the Sponsor in confidence to the Investigator and his/her appointed staff. None of this material may be disclosed to any party not directly involved in the study without written permission from Chiesi.

The Investigator must assure the patient's anonymity will be maintained. The Investigator will keep a separate list with at least the initials, the patient's study numbers, names, and addresses and telephone numbers. The Investigator will maintain this for the longest period of time allowed by his/her own institution and, in any case, until further communication from Chiesi.

21. PREMATURE TERMINATION OF THE STUDY

Both the Sponsor and the Investigator reserve the right to terminate the study at any time. Should this be necessary, the procedures for an early termination or temporary halt will be arranged after consultation by all involved parties.

The Sponsor should submit a written notification to the Regulatory Authority concerned and Ethics Committee/Institutional Review Board providing the justification of premature ending or of the temporary halt.

Clinical Study Code No.: CLI-050000-04	Version No.: 4.0
EUDRACT No.: 2020-002632-75 – IND No: 153286	Date: 02 MAR 2021

22. CLINICAL STUDY REPORT

The clinical study report, including the statistical and clinical evaluations, shall be prepared and sent to the Coordinating Principal Investigator for agreement and signature.

At the end of the trial a summary of the clinical study report will be provided to all Ethics Committees/Institutional Review Boards, to the Competent Authority of the UK and USA concerned and to Investigators.

23. RECORD RETENTION

After completion of the study, all documents and data relating to the study will be kept in an orderly manner by the Investigator in a secure study file.

Regulations require that essential documents must be retained for at least two years after the final marketing approval in an ICH region or until two years have elapsed since the formal interruption of the clinical development of the product under study.

It is the responsibility of the Sponsor to inform the Investigator of when these documents can be destroyed. The Investigator must contact Chiesi before destroying any trial-related documentation. In addition, all patients' medical records and other source documentation will be kept for the maximum time permitted by the institution.

24. PUBLICATION OF RESULTS

Chiesi is entitled to publish and/or present any results of this study at scientific meetings, and to submit the clinical trial data to national and international Regulatory Authorities and, if they fall under the Chiesi commitments on Clinical Trial Transparency, to make them available on www.chiesi.com. Chiesi furthermore reserves the right to use such data for industrial purposes.

In the absence of a Study Steering Committee, Investigators will inform Chiesi before using the results of the study for publication or presentation and agree to provide the Sponsor with a copy of the proposed presentation. Data from individual study sites must not be published separately.

Negative as well as positive results should be published or otherwise made publicly available according to the relevant regulatory requirements.

ITT	Intention-To-Treat
Max	Maximum
MedDRA	Medical Dictionary for Regulatory Activities
Min	Minimum
NIV	Non-Invasive Ventilation
PEEP	Positive End-Expiratory Pressure
PIP	Peak Inspiratory Pressure
Pplat	Plateau Pressure
PT	Preferred Term
RR	Respiratory Rate
rtPCR	Real Time Polymerase Chain Reaction
SAE	Serious Adverse Event
SAP	Statistical Analysis Plan
SBP	Systolic Blood Pressure
SD	Standard Deviation
SDTM	Study Data Tabulation Model
SARS	Severe Acute Respiratory Syndrome
SOC	System Organ Class
SOFA	Sequential Organ Failure Assessment
TA	Tracheal Aspirate
TEAE	Treatment Emergent Adverse Event
TV	Tidal Volume
UK	United Kingdom
vvECMO	Veno-Venous Extracorporeal Membrane Oxygenation

WHO	World Health Organization
WHO-DD	World Health Organization Drug Dictionary

VERSION HISTORY

Version	Date	Change History
0.1	07 Aug 2020	Not Applicable
0.2	01 Oct 2020	Updates following Chiesi review: Add of D21 mortality description, modification of Safety population definition.
0.3 (Stable version)	08 Oct 2020	Minor updates.
0.4	31 Aug 2021	Update according to protocol amendment. Protocol (protocol version 4.0, dated 02 March 2021). 
- The ECMO cohort has been removed- Central Laboratory assessments will be performed only for UK patients- Allowed Time windows have been identified and implemented- Clarify the inclusion of Death as intercurrent event in the primary endpoint- Key secondary endpoint added to comply with FDA request and guideline.- Additional timepoint for assessment added at Day 28 in line with FDA guideline.- New endpoints added to incorporate Death as intercurrent event in the evaluation
0.5	29 Jun 2022	Simplification of the analyses planned due to a lower recruitment. Slight update on footnotes and reference listings.
1.0	27 July 2022	Final version

1 Introduction

This document presents the Statistical Analysis Plan (SAP) for Chiesi Farmaceutici S.p.A. protocol CLI-050000-04: Multicenter, open label, randomised trial to assess the efficacy and tolerability of poractant alfa (porcine surfactant, Curosurf®) in hospitalized subjects with SARS-COV-19 acute respiratory distress syndrome (ARDS).

This analysis plan is based on the protocol (version 4.0), dated 02March2021 and the final electronic case report form (eCRF) (version 4.0) dated 03Jun2021.

The SAP provides the description of the final analyses. In case of deviations from the SAP, explanations will be provided in the Clinical Study Report (CSR).

██████████ will perform the statistical analyses and is responsible for the production and quality control of all outputs described in this document.

2 Study Design

This is a phase 2- proof of concept, multicentre, open-label, randomised study that includes a group of subjects treated with poractant alfa and a control group on standard of care.

Approximately 42 subjects with ARDS due to SARS-COV-19 will be randomized in the poractant alfa group and 28 subjects randomized in the control one.

Date of randomisation is considered Day 1 for both groups. This study consists a total of 28 days, as follows (refer to the Study Schedule in Table 1 for more details):

- Screening: from intubation to randomization (Day 1).
- Treatment period:
 - For poractant alfa group: from Day 1 till Day 3. Subjects receive three poractant alfa endotracheal administrations with a 24 hours interval.
 - For control group: standard of care from randomization on Day 1 till ICU discharge.
- Follow up period:
 - For poractant alfa group: from Day 4 to Day 28.
 - For control group: from ICU discharge to Day 28.

A participant is considered to have completed the study if he/she has completed the last scheduled procedure shown in the schedule of assessments, i.e., follow up at Day 28. The end of the study is defined as the date of the last follow up visit at Day 28 for the last participant in the trial.

Some recruited and treated subjects are likely to be transferred during the study period from the ICU to another hospital department for continuation of their clinical care. In this case the subject will remain in the study and relevant data will still be recorded through review of the medical chart or phone call by the Investigator to the physician of the other department also to check the occurrence of any adverse event as well as of any change in relevant concomitant medications.

The study schedule (Table 1) summarizes the study assessments by study day.

Table 1: Study Schedule

	ICU stay period					ICU discharge	Last FUP
Poractant alfa treated group	Screening ⁷	Day 1 (Randomisation)	Day 2	Day 3	Day 4 – 27	Day X	Day 28
		Before randomisation/treatment and 6-12-24h after each administration up to 72 hours			Every 24h till ICU discharge	Whenever it occurs	
Control group	Screening	Time 72 h			Day 4 – 27	Day X	Day 28
		Before randomisation and at 6, 12, 24, 30, 36, 48, 54, 60, 72 h since randomisation			Every 24h till ICU discharge	Whenever it occurs	
Assessments							
Informed consent	X						
Inclusion and exclusion criteria	X						
Demography	X						

		ICU stay period				ICU discharge	Last FUP
Poractant alfa treated group	Screening ⁷	Day 1 (Randomisation)	Day 2	Day 3	Day 4 – 27	Day X	Day 28
		Before randomisation/treatment and 6-12-24h after each administration up to 72 hours		Every 24h till ICU discharge		Whenever it occurs	
Control group	Screening	Time 72 h		Day 4 – 27		Day X	Day 28
		Before randomisation and at 6, 12, 24, 30, 36, 48, 54, 60, 72 h since randomisation		Every 24h till ICU discharge		Whenever it occurs	
Vital signs (blood pressure, heart rate)	X	Once Treated group: 24 - 48 - 72h post start of treatment Control group: 24 - 48 - 72h post randomisation		X	X	X	X
Full physical examination including height and weight	X						
Medical history (SARS COVID-19 ADRS, past and current relevant medical conditions)	X						
Arterial Blood Gas (ABG) Analysis ¹	X (If the screening assessment is done just before randomization no need to repeat the assessment)	Treated group: Before randomisation and 6-12-24h after each administration up to 72 hours Control group: Before randomisation and at 6, 12, 24, 30, 36, 48, 54, 60, 72h since randomisation		Every 24h	X	Once if not discharged from ICU	
Respiratory support assessment Ventilator parameters ²	X (If the screening assessment is done just before randomization no need to repeat the assessment)	Treated group: Before randomisation and 6-12-24h after each administration up to 72 hours Control group: Before randomisation and at 6, 12, 24, 30, 36, 48, 54, 60, 72h since randomisation		Every 24h	X	Once if not discharged from ICU	

		ICU stay period				ICU discharge	Last FUP
Poractant alfa treated group	Screening ⁷	Day 1 (Randomisation)	Day 2	Day 3	Day 4 – 27	Day X	Day 28
		Before randomisation/treatment and 6-12-24h after each administration up to 72 hours		Every 24h till ICU discharge		Whenever it occurs	
Control group	Screening	Time 72 h		Day 4 – 27		Day X	Day 28
		Before randomisation and at 6, 12, 24, 30, 36, 48, 54, 60, 72 h since randomisation		Every 24h till ICU discharge		Whenever it occurs	
Mechanics Laboratory assessments ³		Treated group : Before randomisation and 12, 24, 48, 72, after first administration Control group : Before randomisation and 12, 24, 48, 72, after randomisation		Treated group : 96h after first administration Control group : 96h after randomisation			
Laboratory assessments ⁴	X			Once Treated group : 24h post last treatment Control group : 72h post randomisation		X	Once if not discharged from ICU
SOFA score ⁵	X			Once Treated group : 24h post last treatment Control group : 72h post randomisation		X	Once if not discharged from ICU
Thoracic CT scan or Chest XR ⁶	X						
Curosurf administration (untreated group)		Three ET administrations with a 24 hours interval (Day 1, Day 2 and Day 3)					
Concomitant Medications	X	X	X	X	X	X	X

	ICU stay period					ICU discharge	Last FUP
Poractant alfa treated group	Screening ⁷	Day 1 (Randomisation)	Day 2	Day 3	Day 4 – 27	Day X	Day 28
		Before randomisation/treatment and 6-12-24h after each administration up to 72 hours			Every 24h till ICU discharge	Whenever it occurs	
Control group	Screening	Time 72 h			Day 4 – 27	Day X	Day 28
		Before randomisation and at 6, 12, 24, 30, 36, 48, 54, 60, 72 h since randomisation			Every 24h till ICU discharge	Whenever it occurs	
Adverse Events	X	X	X	X	X	X	X
Ventilatory support	X	X	X	X	X	X	X
Concomitant procedures	X	X	X	X	X	X	X

- ¹ Arterial blood gas (ABG) analysis: pH, pCO₂, pO₂, HCO₃, lactate.

- ² Ventilatory parameters: PaO₂/FiO₂, FiO₂, TV (tidal volume), RR (respiratory rate), Cstat (static compliance), Cdyn (dynamic compliance), PEEP (positive end-expiratory pressure), PIP (peak inspiratory pressure), Pplat (plateau Pressure).

- ³ For mechanics assessments: blood sampling and tracheal aspirates (TA). Bronchoscopic washings performed as clinically indicated only, with surplus samples retrieved for mechanistic study as available. They are planned only for patients recruited in UK.

- ⁴ Blood count, bilirubin, creatinine, eGFR, glucose, AST, ALT, LDH, D-dimer, CRP (C-reactive protein), procalcitonin. Urine beta HCG at screening only.

- ⁵ SOFA score is calculated considering PaO₂/FiO₂, Glasgow coma scale, mean arterial pressure, and bilirubin, platelet and creatinine levels. SOFA score can be calculated only after the patient is included in the study (after the ICF signature) and in case not all the SOFA parameters are available before randomization, the calculation can be based on historical data collected (within 24 hours) as per standard practice.

- ⁶ Already available as part of the standard care procedures.

- ⁷ All screening procedures have to be completed/Performed before the randomization.

The following time deviations from theoretical post-dose times will be allowed:

Post-dose time assessments	Allowed deviations
≤ 72 hours	± 1 hour
>72 hours	± 2 hours

3 Study Objectives

3.1 Primary Objective

- To evaluate the efficacy and safety of poractant alfa, (porcine surfactant, Curosurf[®]) administered by endotracheal (ET) instillation in terms of ventilatory free days during

the 21 days after randomization, in adult subjects with ARDS due to SARS-COV-19 infection.

3.2 Secondary Objectives

- To evaluate the efficacy and safety of poractant alfa administered by ET Instillation compared to control group, in terms of oxygenation ($\text{PaO}_2/\text{FiO}_2$), FiO_2 , free days from invasive and non-invasive mechanical ventilation, length of ICU stay, mortality at 28 days, SOFA score (overall organ -failure measurement), incidence of AEs, vital signs and laboratory parameters.

3.3 Exploratory Objectives

- To investigate possible mechanism that could impact on surfactant functionality in COVID-19 infected subjects requiring ventilator support: decreased concentration of surfactant phospholipid and protein, altered surfactant phospholipid composition, surfactant protein proteolysis and/or oedema protein inhibition of surfactant surface tension function as a consequence of inflammation.

These exploratory parameters will be assessed only for UK subject enrolled in the study. Given the current pandemic situation and the samples delivery procedures within 48h, it has been deemed appropriate to avoid additional burden for US sites.

4 Study Variables

4.1 Efficacy Variables

4.1.1 Primary Efficacy Variable

The primary efficacy variable is the number of days alive and ventilator-free defined as the number of days the subjects is alive and not receiving mechanical ventilation over the **21 days** following randomisation.

Mechanical ventilation is defined as invasive and non-invasive. Subject is defined as free of mechanical ventilation after 12 hours from the suspension of either invasive or non-invasive ventilation. Subjects who die or are mechanically ventilated longer than this period are assessed as zero ventilator-free days.

4.1.2 Secondary Efficacy Variables

4.1.2.1 Key Secondary Efficacy Variable

- Percentage of subjects alive and free of respiratory failure (i.e., need for mechanical ventilation, ECMO, non-invasive ventilation, or high-flow nasal cannula oxygen delivery) **at Day 28**.

4.1.2.2 Others Secondary Efficacy Variables

- Number of days alive and ventilator-free **at Day 28**
- Mortality **at Day 21 and Day 28**
- Number of days alive and free from invasive ventilation **at Day 21 and Day 28**

- Number of days alive and free from non-invasive ventilation (NIV) at **Day 21 and Day 28**
- Percentage of subjects with improvement in severity status defined as a decrease in the severity score at **Day 28 or Discharge**, whichever comes first. Severity score will be defined as Mild, Moderate, Severe or Death based on PaO₂/FiO₂ ratio and subject status at Day 28 and numerically rated from 1-4 respectively:

Severity	Variable	Criteria
Mild -1	PaO ₂ /FiO ₂ Ratio	200 mmHg < PaO ₂ /FIO ₂ ≤ 300 mmHg
Moderate - 2	PaO ₂ /FiO ₂ Ratio	100 mmHg < PaO ₂ /FIO ₂ ≤ 200 mmHg
Severe - 3	PaO ₂ /FiO ₂	Ratio PaO ₂ /FIO ₂ ≤ 100 mmHg
Death - 4	Patient Status	Yes/No

- Change from baseline in PaO₂/FiO₂ ratio at **6 and 12 hours following administration of each dose** in the treated group and at the similar timepoints in the control group (6, 12, 30, 36, 54 and 60 hours after randomisation)
- Change from baseline in PaO₂/FiO₂ ratio at additional timepoints (i.e. every 24 hours after treatment/randomisation until the subject is discharged from the ICU)
- Percentage of subjects alive and with PaO₂/FiO₂ improvement of >20% at **6 and 12 hours following administration of each dose** in the treated group and at similar timepoints in the control group (6, 12, 30, 36, 54 and 60 hours after randomisation)
- Percentage of subjects alive and with PaO₂/FiO₂ improvement of >20% at the additional timepoints (i.e. every 24 hours after treatment/randomisation till the subject is discharged from the ICU)
- Change from baseline in FiO₂ at **6 and 12 hours following administration of each dose** in the treated group and at similar timepoints in the control group (6, 12, 30, 36, 54 and 60 hours after randomisation)
- Change from baseline in FiO₂ at additional timepoints (i.e. every 24 hours after treatment/randomisation until the subject is discharged from the ICU)
- Length of ICU stay (days) **at Day 28**. Subjects who die or are mechanically ventilated longer than this period are assigned with 28 days
- Percentage of subjects alive and out of ICU **at Day 28**
- Delta SOFA Score and sub-score component measured on **Day 3 and Day 28 or Discharge** whichever comes first
- Percentage of subjects alive and organ failure free (SOFA score=0) at **Day 28 or Discharge** whichever comes first
- Change from baseline in ventilatory parameters [tidal volume (TV), respiratory rate (RR),dynamic compliance (Cdyn), static compliance (Cstat), positive end-expiratory pressure (PEEP), peak inspiratory pressure (PIP), plateau pressure (Pplat)] measured at 6-12-24h after each poractant alfa administration up to 72 hours and at similar

timepoints in the control group (6, 12, 24, 30, 36, 48, 54, 60 and 72 hours after randomisation) and then every 24 hours till the subject is discharged from the ICU

- Change from baseline in blood gas analysis acid-base balance parameters (i.e. pH, pCO₂, pO₂, HCO₃, lactate) measured at 6-12-24h after each poractant alfa administration up to 72 hours and at similar timepoints in the control group (6, 12, 24, 30, 36, 48, 54, 60 and 72 hours after randomisation) and then every 24 hours till the subject is discharged from the ICU

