7.2 Intercurrent Events

Death and Early discontinuation from study drug can be anticipated as intercurrent events:

- Death will be incorporated as a failure outcome for binary endpoints using composite strategy;
- Early discontinuation from study drug will be handled using treatment policy strategy: all data collected after discontinuation from study drug till Day 28 or death will be included;
- Change in respiratory parameters will be analysed using while-alive strategy.

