9.3.4 Improvement in Severity Status at Day 28 or Discharge

The severity status will be based on the ventilatory parameters form for PaO₂/FiO₂ ratio at baseline and at Day 28 or Discharge (whichever comes first) and on Study Termination form for the death, according to the scale below:

Severity	Variable	Criteria
Mild - 1	PaO ₂ /FiO ₂ Ratio	200 mmHg < PaO ₂ /FIO ₂ ≤ 300 mmHg
Moderate - 2	PaO ₂ /FiO ₂ Ratio	100 mmHg < PaO ₂ /FIO ₂ ≤ 200 mmHg
Severe - 3	PaO ₂ /FiO ₂	Ratio PaO ₂ /FIO ₂ ≤ 100 mmHg
Death - 4	Patient Status	Yes/No

In case of multiple assessments done on same date, the last assessment will be taken into account for the severity status definition.

The severity status, the number and percentage of subjects with an improvement (i.e. a decrease of at least one point of severity) from baseline to Day 28 or Discharge will be summarized. A shift table displaying the severity at baseline and at day 28 or Discharge will also be provided.

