9.3.10 Change from Baseline in SOFA Score

SOFA sub-score and total score actual values and change from baseline will be presented using descriptive statistics at Day 3, ICU discharge or Day 28 (whichever comes first).by treatment group. The change from baseline to Day 3 and to ICU Discharge or Day 28 difference between the two groups for each sub-score and for total score will be described.

A graph displaying the means and SD for each timepoint (until the subject is discharged from ICU) will be also provided for each treatment group.

9.3.11 Percentage of Subjects Alive and Organ Failure Free (SOFA score=0) at Day 28 or Discharge

The subject will be defined alive and organ failure free at Day 28 or Discharge if:

- Date of Death is missing or > MIN (Date of Day 28 or Date of Discharge)

AND

- Total SOFA Score = 0 at Day 28 or at Discharge

The percentage will be summarized.

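### SAP 9.3.11 counts a patient who leaves the ICU with SOFA 0 and dies before Day 28 as alive and organ failure free; for the same patient, the severity endpoint has no rule on whether death prevails

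*SAP*

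**What the plan says.** **Death in general.** SAP 7.2, like protocol 12.3, states: "Death will be incorporated as a failure outcome for binary endpoints using composite strategy". It gives no time limit.

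**Organ failure free (SAP 9.3.11).** Two conditions must both hold. The survival condition is "Date of Death is missing or > MIN (Date of Day 28 or Date of Discharge"). The SOFA condition is "Total SOFA Score = 0 at Day 28 or at Discharge". Discharge here means discharge from the ICU: SAP 9.3.10 presents the SOFA score "at Day 3, ICU discharge or Day 28 (whichever comes first"), and the schedule collects SOFA at ICU discharge.

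**Severity (SAP 4.1.2.2 and 9.3.4).** Improvement is a fall in a score of 1 to 4, judged at the earlier of discharge and Day 28. SAP 4.1.2.2 bases the score on the PaO₂/FiO₂ ratio and "subject status at Day 28 and numerically rated from 1-4 respectively". SAP 9.3.4 takes the "ratio at baseline and at Day 28 or Discharge (whichever comes first") and relies "on Study Termination form for the death, according to the scale below". It gives no cut-off date for the death and no rule on which source prevails.

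**Follow-up.** SAP section 2 keeps subjects in the study after they leave the ICU, up to Day 28. Deaths after ICU discharge are therefore observed.

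**The concern.** If a patient leaves the ICU in good condition and dies before Day 28, SAP 7.2 suggests a failure. The formula in 9.3.11 gives a success. The version history says endpoints were added so that death would enter the evaluation as an intercurrent event, and for deaths after discharge the formula works against that purpose.

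The cut-off is also a post-randomisation event. A patient still in the ICU can fail by dying on any day to Day 28, while a patient discharged on Day 10 can fail by dying only up to Day 10. The window may thus depend on something the treatment could influence.

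For severity, the patient's result depends on which of two instructions the programmer follows.

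**Working it through.** The plan gives no figure for either endpoint, and its one design calculation (84% power for ventilator-free days) is not involved. The check is to apply the written rules to one patient and then work out what one patient is worth.

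**Illustrative patient (assumed values).** PaO₂/FiO₂ 80 at baseline; ICU discharge on Day 10 with SOFA 0 and PaO₂/FiO₂ 250; death on Day 20.

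**Organ failure free, SAP 9.3.11**
- Cut-off: MIN(28, 10) = 10.
- Survival condition: 20 > 10 is true.
- SOFA condition: 0 at discharge, true.
- Result: alive and organ failure free.
- With survival required through Day 28: 20 > 28 is false, so failure.
- Days to Day 28 on which this patient's death would not count as failure: 28 − 10 = 18. For a patient still in the ICU at Day 28: none.

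**Severity, SAP 4.1.2.2 and 9.3.4**
- Baseline: 80 ≤ 100, score 3.
- Status read at the earlier of discharge and Day 28: 200 < 250 ≤ 300, score 1. The change is 3 to 1, improved.
- Status read at Day 28, or any death on the Study Termination form taking precedence: score 4. The change is 3 to 4, not improved.
- The Day 28 status wording in 4.1.2.2 and the undated death source in 9.3.4 both favour the second result. Only the timing phrase supports the first.

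**Comparison with other binary endpoints in the SAP**

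| Section | When survival is judged |
|---|---|
| 9.2 Free of respiratory failure | Day 28 visit |
| 9.3.9 Out of ICU | Day 28 visit |
| 9.3.6 PaO₂/FiO₂ improvement >20% | Before the analysis timepoint |
| 9.3.11 Organ failure free | Earlier of discharge and Day 28 |
| 9.3.4 Severity | Not stated |

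Listing 16.2.6.2-b has value columns for Baseline, D21 and D28 only. The illustrative patient could be shown there as dead and as alive and organ failure free by Day 28.

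**Size.** Shift in an arm's rate = 100 × k / n, where k is the number of reclassified patients. Planned n is 42 and 28 (SAP section 5); k is not given, so 1 to 3 is an assumed range.

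| k (assumed) | n = 42 | n = 28 |
|---|---|---|
| 1 | 2.4 points | 3.6 points |
| 2 | 4.8 points | 7.1 points |
| 3 | 7.1 points | 10.7 points |

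SAP section 12 says recruitment closed before 70, and 7.4 leaves missing values out of denominators. The real n is therefore smaller and the shift per patient larger. For the same reason, the number of such patients is likely to be lower.

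**The case against.** The best defence is that 9.3.11 implements the endpoint as written. Protocol section 8 and SAP 4.1.2.2 both define it at the earlier of Day 28 and discharge, and MIN expresses that timing. On this view a death after the assessment is not an intercurrent event for a status already read. SAP 9.3.6, which fails only subjects who die before the analysis timepoint, shows the composite strategy applied with such a limit.

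Part of this stands. The formula is not a slip against the protocol's timing, and 7.2 and 9.3.11 can be reconciled on that narrow reading. The analogy is incomplete, however. The timepoints in 9.3.6 are scheduled, whereas here the cut-off is each patient's own ICU discharge.

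The objection on severity is stronger. A reader might infer that a patient who dies after discharge is scored as improved. The documents do not establish that: the Day 28 status clause and the undated source, "and on Study Termination form for the death", point to a score of 4.

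It is also fair to say that mortality at Day 21 and Day 28 is reported separately (9.3.2), that a discordant patient would be visible in the listing, and that the protocol's models for both endpoints were dropped.

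**Conclusion.** The point holds for 9.3.11. As written, the rule classes a patient with SOFA 0 at ICU discharge who dies by Day 28 as alive and organ failure free. That sits against the unlimited wording of 7.2 and makes the window for counting deaths depend on discharge date. For severity the finding is an ambiguity that leans towards Death (4).

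One patient is worth 2.4 or 3.6 points at planned size, and more at the actual size. Only deaths after discharge with SOFA 0 are affected in 9.3.11. The documents give neither their number nor the final arm sizes, so no total effect can be stated. A reader might also infer that the rule favours the arm with earlier discharges. That is possible in principle, but nothing in the documents shows a difference in discharge timing.

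Both are non-key secondary endpoints, summarised only by descriptive statistics. No test depends on them, but with description alone the classification of each patient is the reported result.

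**What to change.** - **SAP 9.3.11:** replace the survival condition with alive through Day 28, so that death on or before Day 28 is a failure whether or not the patient was discharged first. Keep SOFA at the earlier of ICU discharge and Day 28.
- **SAP 9.3.4:** state that death on or before Day 28 takes precedence over the PaO₂/FiO₂ category and is scored 4.
- **SAP section 12:** record both as a clarification of the protocol's timing wording. If the SAP is not reopened, section 1 allows the deviation to be explained in the clinical study report.

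No new data are needed. Day 28 follow-up takes place on the unit or by phone, and 9.3.8 already uses a recorded death date. The cost is that responder rates may be slightly lower and the endpoint wording departs slightly from the protocol. The revised text should also say how a subject with unknown Day 28 vital status is handled; under the general rule in 7.4 the value would be missing.
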